**Table 11-1 Analysis Visit Windows for Safety and Efficacy Assessments**

Assessment	Visit 	Target Study Day	Analysis Visit Window  (in study days)

Then, age (in years) at first dose or nominal visit = [(first dose date or nominal visit date – informed consent date) in days + age at informed consent (in days)]/365.25.
 
2. Age (in months) at nominal visit (for calculation of BMI and z-scores, as applicable):
 
Obtain the age at informed consent (in months) in “yy, mm” format (e.g., 24 years, 6 months) from the VS page at the Screening Visit.
 
Obtain the informed consent date.
 
Then, age (in months) at nominal visit = integer part of {[age at informed consent (in months) + 0.5 + diff (nominal, informed consent date) in months]} + 0.5.
 
3. Missing first dose date or last dose date:
 
If the first dose date is missing, use the Day 1 visit date to impute.
 
If the last dose date is missing or a partial date is reported, the last dose date will be imputed based on, in descending order of priority, the ETT visit date, the last visit date before the Safety Follow-up visit, or the last study drug administration date from the EC SDTM domain, as appropriate. The imputation algorithm will ensure the imputed last dose date does not exceed the study participation end date.
 
4. Sweat Chloride:
 
Non-missing sweat chloride concentrations from the left arm and right arm with assessment end date/time for a given arm up to 30 minutes after the first dose time in the Treatment Period will be considered for baseline.
 
5. Electrocardiogram:
 
Baseline is defined as the most recent pre-treatment measurement before the first dose of study drug in the Treatment Period. If multiple ECG measurements are obtained on the same calendar day during the TE Period for the Treatment Period,
 
 
○ For summary purposes, the calculated average ECG will be used as the ECG value on that day;
 
○ For threshold analysis purposes, all reported ECG values will be used.
 
			

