#### **9.1.5 Early Termination of Treatment**

If a subject prematurely discontinues study drug treatment, an Early Termination of Treatment (ETT) Visit should be scheduled as soon as possible after the decision to discontinue treatment. Subjects who prematurely discontinue treatment will also be required to complete the Safety Follow-up Visit, approximately 28 ( $\pm$  7) days after their last dose of study drug.

If the ETT Visit occurs 3 weeks or later following the last dose of study drug, then the ETT Visit will replace the Safety Follow-up Visit, and a separate Safety Follow-up Visit will not be required.

If a subject withdraws consent for the study, no further assessments will be performed. Vertex may retain and continue using the study data and samples after the study ends, and may use the samples and information in the development of the study compound, for other drugs and diagnostics, in publications and presentations, and for education purposes. If a subject withdraws from the study, the study data and samples collected will remain part of the study (Section 9.9).

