##### **9.1.5.2 Discontinuation During the Treatment Period**

Subjects who prematurely discontinue study drug treatment during the Treatment Period should continue to complete all scheduled study visits for assessments following completion of the ETT Visit (and Safety Follow-up Visit, if applicable), as detailed in Table 3-2.

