#### **Baseline value:**

For all safety endpoints:

- Unless otherwise specified, baseline will be defined as the most recent non-missing measurement (scheduled or unscheduled) collected before the first dose of study drug in the Treatment Period (i.e., the Day 1 Visit).

For all efficacy endpoints:

- Except for SwCl, baseline will be defined as the pre-dose Day 1 value. If the pre-dose Day 1 value is missing, the most recent pre-dose, non-missing value on or after the Day -14 visit, including unscheduled visits, will be used as baseline.
- For SwCl, baseline will be defined as the average of the two most recent pre-dose, non-missing values on or after the Day -14 visit, including unscheduled visits. If only 1 non-missing value is available during this interval, the available value will be considered as baseline.

**Absolute change** from baseline will be calculated as post-baseline value - baseline value.

**Relative change** from baseline will be calculated as (post-baseline value - baseline value)/baseline value.

The **Treatment-emergent (TE) Period for the Run-in Period** will be from the first dose date of study drug in the Run-in Period to (1) the first dose date of study drug in the Treatment Period for subjects who complete the Run-in Period and continue to the Treatment Period, or (2) 28 days after the last dose date of study drug in the Run-in Period or to the completion of study participation date, whichever occurs first, for subjects who do not continue to the Treatment Period (e.g., subjects who do not meet the conditions to enter the Treatment Period).

The **TE Period for the Treatment Period** will be from the first dose date of study drug in the Treatment Period (VNZ/TEZ/D-IVA or ELX/TEZ/IVA) to 28 days after the last dose date of study drug in the Treatment Period or to the completion of study participation date, whichever occurs first.

The **PEx analysis period through Week 52** will be from the first dose date of study drug in the Treatment Period to the last efficacy assessment, which may be collected up to the Week 52 Visit or the earlier of Day 365 and the completion of study participation date if a subject does not have the Week 52 Visit.

**Unscheduled visits:** Unscheduled visit measurements will be included in analysis as follows:

- 1) In scheduled visit windows per specified visit windowing rules
- 2) In the derivation of baseline and last on-treatment measurements

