### 8.3.1.4 Supplementary Analysis

#### 8.3.1.4.1 Alternative Estimand using Hypothetical Strategy

An alternative estimand will be defined similarly to the primary estimand with the exception that ICE will be addressed using the hypothetical strategy. In the hypothetical strategy, observed values after ICE will be set to missing to provide a conservative and robust test of non-inferiority for the primary endpoint. Supplementary analysis of this alternative estimand will be performed similarly to the primary analysis as specified in 8.3.1.3. Additional details are presented in [Appendix](#) .

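### The SAP's rule for a missing or partial last dose date prefers visit dates to recorded data, so it can set a date later than the true one and contradict a reported month.

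*SAP*

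**What the plan says.** SAP Appendix A, Derived Variables item 3, covers a last dose date that is missing or only partly reported. Its first choice is the ETT visit: "the last dose date will be imputed based on, in descending order of priority, the ETT visit date". The remaining choices are "the last visit date before the Safety Follow-up visit, or the last study drug administration date from the EC SDTM domain, as appropriate". One limit is stated: "The imputation algorithm will ensure the imputed last dose date does not exceed the study participation end date".

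Protocol 9.1.5 says that the ETT visit "should be scheduled as soon as possible after the decision to discontinue treatment". It gives no maximum interval, and it plans for a long one: "If the ETT Visit occurs 3 weeks or later following the last dose of study drug", the ETT visit replaces the Safety Follow-up Visit. Under Protocol 9.1.5.2, subjects who stop drug during the Treatment Period "should continue to complete all scheduled study visits for assessments following completion of the ETT Visit".

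Three SAP definitions use the last dose date:
- Exposure (8.2.5) is last dose date minus first dose date plus 1.
- Compliance (8.2.6) has exposure duration as its denominator.
- The TE Period for the Treatment Period (8.1) runs "to 28 days after the last dose date of study drug in the Treatment Period", or to completion of study participation if that is earlier.

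**The concern.** The first-choice substitute is a visit that follows the decision to stop, so any error from it runs one way: the imputed date falls on or after the true last dose. The second choice need not lie close to the last dose either, because discontinued subjects go on attending visits. For the same reason the participation cap often lies well beyond the ETT visit and does not bind.

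The partial-date case is the clearest. If a site reports the month and year of the last dose but not the day, item 3 still substitutes a visit date and does not require it to fall in that month. The SAP treats other partial dates differently. Appendix B completes a medication stop date within the known month or year. Appendix E keeps the known month and year of an adverse event start date. Only the study drug stop date can lose information that was recorded.

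At stake are exposure, the compliance categories, and which adverse events, laboratory values and concomitant medications count as falling in the TE Period. The subjects affected are mainly early discontinuers, for whom timing relative to stopping matters most.

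**Working it through.** The plan states no figure that depends on this rule, so there is none to reproduce. The check applies the SAP's own definitions to an example.

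**Inputs.** First dose is Day 1 and the true last dose is Day 100 (example). The lag from last dose to ETT is assumed; 21 days is the interval named in Protocol 9.1.5. Exposure = last − first + 1 (SAP 8.2.5). Compliance = 100 × (1 − interruption days / exposure) (SAP 8.2.6). TE end = the earlier of last dose + 28 and participation end (SAP 8.1).

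**Exposure, lag 21.** True: 100 − 1 + 1 = 100 days. Imputed: 121 − 1 + 1 = 121 days. The error equals the lag, and is 0 if ETT falls on the day of the last dose.

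**Compliance, lag 21, 21 interruption days (example).** True: 100 × (1 − 21/100) = 79.0%. Imputed: 100 × (1 − 21/121) = 82.6%. The subject crosses the SAP's 80% category boundary.

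**TE Period end.**

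| Lag (days) | Participation ends | True TE end | Imputed TE end | Shift (days) |
|---|---|---|---|---|
| 21 | Day 365 | 100 + 28 = Day 128 | 121 + 28 = Day 149 | +21 |
| 21 | at ETT, Day 121 | Day 121 | Day 121 | 0 |
| 21 | at Safety Follow-up, Day 128 | Day 128 | Day 128 | 0 |
| 35 | Day 365 | Day 128 | 135 + 28 = Day 163 | +35 |
| 35 | at ETT, Day 135 | Day 128 | Day 135 | +7 |

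The TE end therefore moves by the full lag for a subject who stays in follow-up. It does not move, for lags up to 28 days, when participation ends at ETT or at a Day 128 follow-up.

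**Reported month.** In a 31-day month with a 21-day lag, a true stop on day 11 or later (11 + 21 = 32) gives an imputed date in the next month.

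**Completers.** Protocol Table 3-2 ends dosing on the evening before the Week 52 Visit, so imputing that visit date adds 1 day.

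**Total size.** No document gives the number of missing or partial last dose dates. The planned 10% drop-out at Week 24 is about 0.10 × 550 = 55 subjects. Assume that 1% to 20% of them lack a complete date, with lags of 7 to 28 days:
- Low: 0.55 × 7 = 3.9 patient-days; 3.9 / 550 = 0.01 day of mean exposure.
- High: 11 × 28 = 308 patient-days; 308 / 550 = 0.56 day of mean exposure.

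Even 5% of all randomized subjects (27.5, rounded up to 28) at 28 days gives 784 patient-days. Against 550 × 364 = 200,200, that is 0.39%.

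**Would putting EC first be safe?** The documents do not describe what EC contains. Protocol 9.6.1 requires dose dates only for the two doses before a PK sample and that morning's dose. Table 3-2 schedules PK samples through Week 24 and at ETT. If EC holds only those doses, a subject with no ETT record who dosed to Day 364 would be dated at Day 169, which is 364 − 169 = 195 days too early.

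**The case against.** The other side has substantial points.

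- **The ETT visit is meant to be prompt.** Three weeks or more is a contingency, and the error is zero when ETT falls on the last dose day. This stands: the rule can date too late, but does not always do so.
- **The order is qualified as applying where appropriate.** This leaves room for judgement. It does not say when to depart from the order, and it does not require agreement with a reported month.
- **Ranking EC last may be deliberate.** Given the 195-day example, this stands against a plain reversal of the order. It is no reason to ignore EC as a lower bound.
- **A late date is cautious for safety.** A wider TE window counts more events as treatment-emergent, as the SAP already does for events with unclear start dates. Safety is descriptive and no exposure-adjusted adverse event rates are planned, so overstated exposure dilutes no such rate. This stands, but the exposure and compliance summaries are still wrong for the subjects concerned.

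A reader might also infer that the discontinuation event itself is dated too late, so that off-drug spirometry enters the non-inferiority test. The documents do not support this. The primary estimand uses treatment policy (SAP 8.3.1.2), so observed values after discontinuation are used whatever the date. Only the supplementary hypothetical analysis, where "observed values after ICE will be set to missing", depends on when the event occurred. SAP 8.3.1.4.1 and Appendix D do not say which date defines it. If the imputed last dose date were used, some off-drug values, including ETT spirometry, could be kept; that is conditional.

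**Conclusion.** The point holds in limited form. Followed as written, item 3 can give a last dose date later than the true one and in a different month from the one reported. For an affected subject, exposure is overstated by the whole lag and compliance rises with it. The TE Period end moves later only where the participation date does not cap it, so the move from Day 128 to Day 149 should not be read as the general case.

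The primary analysis is unaffected. An effect on the supplementary hypothetical analysis cannot be established from the text. The total effect is probably small, 0.01 to 0.56 days of mean exposure, but that range rests on assumed frequencies and lags. The case for a change is that the rule can contradict recorded data in an avoidable, one-directional way, and that the correction is cheap. It is not that any main result is at risk.

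**What to change.** Rewrite Appendix A item 3 along these lines:

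1. Where a complete stop date is documented, use it first.
2. For a partial date, keep the imputed date within the reported month and year.
3. In all cases, make the imputed date no earlier than the last administration recorded in EC, and no later than the earlier of the ETT visit and the end of study participation.
4. Use visit dates only as a fallback or upper bound within those limits.

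Do not simply move EC to first place: an incomplete EC record would then date the last dose too early and shorten the TE Period. Separately, add one sentence to SAP 8.3.1.4.1 or Appendix D stating which date defines the discontinuation intercurrent event.

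The cost is a paragraph of SAP text and a small change to one derivation, made before database lock. No new data are needed, and there is no real downside.

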## Appendix B: Imputation Rules for Missing Prior/Concomitant Medication Dates

Imputation rules for missing or partial medication start/stop dates are defined below:

1. Missing or partial medication start date:
  - a. If only DAY is missing, use the first day of the month.
  - b. If DAY and Month are both missing, use the first day of the year.
  - c. If DAY, Month, and Year are all missing, use a date before the first dose date (in practice, use the informed consent date to impute).
2. Missing or partial medication stop date:
  - a. If only DAY is missing, use the last day of the month.
  - b. If DAY and Month are both missing, use the last day of the year.
  - c. If DAY, Month, and Year are all missing, assign ‘continuing’ status to stop date (in practice, use the End of Study Date to impute).

In summary, the prior, concomitant, or post categorization of a medication is described below.

**Table 11-2 Prior, Concomitant, and Post Categorization of a Medication**

Medication Start Date	Medication Stop Date			
	< First Dose Date of Run-in TE Period	≥ First Dose Date of Run-in TE Period and < End Date of Run-in TE Period	≥ First Dose Date of Treatment TE Period and ≤ End Date of Treatment TE Period	> End Date of Treatment TE Period
< First Dose Date of Run-in TE Period	P	PC1	PC1C2	PC1C2A
≥ First Dose Date of Run-in TE Period and < End Date of Run-in TE Period	-	C1	C1C2	C1C2A
≥ First Dose Date of Treatment TE Period and ≤ End Date of Treatment TE Period	-	-	C2	C2A
> End Date of Treatment TE Period	-	-	-	A

P: Prior; C1: Concomitant during the Run-in Period; C2: Concomitant during the Treatment Period; A: Post

The same imputation rules will be followed to address missing and/or partial dates for non-pharmacological treatments/procedures.

### Appendix C: Details of GLI Equations for Calculating ppFEV1

Percent predicted values will be calculated for the parameters of FEV1, FVC, FEV1/FVC, and FEF25%-75% using the Quanjer GLI-2012 Regression Equations and Lookup Tables.

The regression equations and lookup tables required to implement the Quanjer GLI-2012 predicted values are available in:

Philip H. Quanjer, Sanja Stanojevic, Tim J. Cole, Janet Stocks. Quanjer GLI-2012 Regression Equation and Lookup Tables. Global Lung Function Initiative. [online] Available at: <https://www.ers-education.org/lr/show-details/?idP=138978> [Accessed Sep 2023].

The instructions and tools on how to implement the Quanjer GLI-2012 equations are:

Philip H. Quanjer, Sanja Stanojevic, Tim J. Cole, Janet Stocks. Implementing GLI-2012 regression equations. Global Lung Function Initiative. [online] Available at: <https://www.ers-education.org/lr/show-details/?idP=138979> [Accessed Sep 2023].

Sanja Stanojevic. GLI-2012 - SAS Macro. Global Lung Function Initiative. [online] Available at: <https://www.ers-education.org/lr/show-details/?idP=138988> [Accessed Sep 2023].

The data handling rule for spirometry is as follows:

- Input age with at least 2 decimal places
- Use height at screening, regardless of if height is collected at other study visits, for subjects whose age at informed consent is >21 years. For subjects with age ≤21 years, height collected at the respective visit should be used.
- For race, race is Black if, on the CRF, Black or African American is the only race selected. Race is Northeast Asian if Northeast Asian is the only race selected. Race is Southeast Asian if Southeast Asian is the only race selected. Race is White if White is the only race selected. Race is Other for all other races, including multiple selections.

**Appendix D: Estimand Framework for the Primary Efficacy Endpoint**

Estimand	Primary Estimand	Alternative Estimand
Treatment	VNZ/TEZ/D-IVA versus ELX/TEZ/IVA	
Population	Study population represented by inclusion and exclusion criteria	
Variable	Absolute change from baseline in ppFEV 1 through Week 24	
Population-level summary	Difference in variable means between VNZ/TEZ/D-IVA and ELX/TEZ/IVA groups	
Handling of ICE		
Treatment discontinuation	Treatment Policy (i.e., observed ppFEV 1 values after the ICE will be used, if available)	Hypothetical strategy (i.e., observed ppFEV 1 values after the ICE will be set to missing)
Use of prohibited medication †		
Analysis	Primary Analysis	Supplementary Analysis
Analysis model	MMRM	
Intermittent missing	MMRM	
Treatment discontinuation	MMRM	
Use of prohibited medication	MMRM	
Other reasons	MMRM	

D-IVA: deutivacaftor; ELX: elexacaftor; ICE: intercurrent event; IVA: ivacaftor; MMRM: mixed model for repeated measures; TEZ: tezacaftor; VNZ: vanzacaftor

† Prohibited medication includes use of non-study drug CFTR modulators for >3 days in either the Run-in Period or the Treatment Period prior to Week 24

## Appendix E: Imputation Rules for Missing AE Dates

Imputation rules for missing or partial AE start date are defined below. If the imputed AE start date is before the informed consent date, the AE start date will be imputed using the study informed consent date.

- **If only Day of AE start date is missing:**

- If the full (or partial) AE end date is NOT before the first dose date in the Treatment Period or AE end date is missing, then
  - if AE start year and month are equal to the month and year of first dose date in the Treatment Period, then impute the AE start day as the day of first dose date in the Treatment Period;
  - else, if AE start year and month are equal to the month and year of first dose date in the Run-in Period, then impute the AE start day as the day of first dose date in the Run-in Period;
  - else, impute the AE start day as 1.
- Else, if the full (or partial) AE end date is NOT before the first dose date in the Run-in Period, then
  - if AE start year and month are equal to the month and year of first dose date in the Run-in Period, then impute the AE start day as the day of first dose date in the Run-in Period;
  - else, impute the AE start day as 1.
- Else, impute the AE start day as 1.

Compare the imputed AE start date with the TE Period to determine whether the AE is pretreatment AE, TEAE during the Run-in Period, TEAE during the Treatment Period, or post-treatment AE.

- **If Day and Month of AE start date are missing:**

- If the full (or partial) AE end date is NOT before the first dose date in the Treatment Period or AE end date is missing, then
  - if AE start year is equal to the year of first dose date in the Treatment Period, then impute the AE start month and day as the month and day of first dose date in the Treatment Period;
  - else, if AE start year is equal to the year of first dose date in the Run-in Period, then impute the AE start month and day as the month and day of first dose date in the Run-in Period;
  - else, impute the AE start month as January and day as 1.
- Else, if the full (or partial) AE end date is NOT before the first dose date in the Run-in Period, then

- if AE start year is equal to the year of first dose date in the Run-in Period, then impute the AE start month and day as the month and day of the first dose date in the Run-in Period;
- else, impute the AE start month as January and day as 1.
- Else, impute the AE start month as January and day as 1.

Compare the imputed AE start date with the TE Period to determine whether the AE is pretreatment AE, TEAE during the Run-in Period, TEAE during the Treatment Period, or post-treatment AE.

- **If Year of AE start date is missing:**

If the year of AE start date is missing or AE start date is completely missing:

- If the full (or partial) AE end date is NOT before the first dose date in the Treatment Period or AE end date is missing, then impute the AE start date as the date of first dose date in the Treatment Period.
- Else, if the full (or partial) AE end date is NOT before the first dose date in the Run-in Period, then impute the AE start date as first dose date in the Run-in Period.
- Else, impute AE start date as the informed consent date.

All imputation should ensure that the imputed AE start date is not before the informed consent date.

Imputation rules for partial AE end dates are defined below:

For a partial AE end date, impute as min (the last day of the month, end of study participation) if day is missing, or min (Dec, end of study participation) if month is missing.

## Appendix F: Criteria for Threshold Analysis

**Table 11-3 Threshold Analysis Criteria for Laboratory Tests (as applicable)**

Parameter	Threshold Analysis	Comments
Clinical Chemistry (LFT)		
ALT	>ULN - ≤3xULN >3x - ≤ 5xULN >5x - ≤ 8xULN >8x - ≤ 20xULN >20xULN	FDA DILI Guidance Jul 2009.
AST	>ULN - ≤3xULN >3x - ≤ 5xULN >5x - ≤ 8xULN >8x - ≤ 20xULN >20xULN	FDA DILI Guidance Jul 2009.
ALT or AST	(ALT>ULN - ≤ 3xULN) or (AST>ULN - ≤ 3xULN) (ALT>3x - ≤ 5xULN) or (AST>3x - ≤ 5xULN) (ALT>5x- ≤ 8xULN) or (AST>5x - ≤ 8xULN) (ALT>8x - ≤ 20xULN) or (AST>8x - ≤ 20xULN) ALT>20xULN or AST> 20xULN	FDA DILI Guidance
Alkaline Phosphatase	>ULN - ≤ 1.5xULN >1.5x - ≤ 2.5xULN >2.5x - ≤ 5x ULN >5x - ≤ 20x ULN >20x ULN	FDA DILI Guidance Jul 2009.
Total Bilirubin	>ULN - ≤ 1.5xULN >1.5x - ≤ 2xULN >2x - ≤ 3xULN >3x - ≤ 10xULN >10xULN	FDA DILI Guidance Jul 2009.
Direct Bilirubin	>ULN - ≤ 1.5xULN >1.5x - ≤ 2xULN >2x - ≤ 3xULN >3x - ≤ 10xULN >10xULN	FDA DILI Guidance Jul 2009.
Indirect Bilirubin	>ULN - ≤ 1.5xULN >1.5x - ≤ 2xULN >2x - ≤ 3xULN >3x - ≤ 10xULN >10xULN	FDA DILI Guidance Jul 2009.
ALT and Total Bilirubin	ALT>3xULN and TBILI>2xULN	FDA DILI Guidance Jul 2009.
AST and Total Bilirubin	AST>3xULN and TBILI>2xULN	FDA DILI Guidance Jul 2009.
(ALT or AST) and Total Bilirubin	(ALT>3xULN or AST>3xULN) and TBILI>2xULN	FDA DILI Guidance Jul 2009.

